## 5.2 Pre-Enrollment Medical Screening

Informed consent must be obtained prior to pre-enrollment medical screening. Investigators who are listed on US “Food and Drug Administration (FDA) Form 1572” or Canadian “Clinical Trial Site Information Form” are authorized to obtain informed consent. Pre-enrollment medical screening is used to determine the eligibility of each candidate. All enrollment evaluations must be performed within the time frame listed below, prior to CPI-613 treatment and include:

Within 2 weeks:

- Bone marrow biopsy or cytologic evidence of relapsed or refractory AML or granulocytic sarcoma
- Optional blood, plasma and bone marrow biopsy sample for biomarker evaluation
- a complete medical history
- physical exam, including vital signs, height, and weight
- ECOG PS
- baseline evaluation of symptoms and medications
- clinical chemistry (including renal function), hematology and coagulation (see Section 5.6 for specifics)

Within 1 week:

- a pregnancy test for women of child-bearing potential (performed within 1 week prior to CPI-613 treatment)

## 5.3 CPI-613 Dosing

This is a Pilot trial to determine the feasibility of CPI-613 given with high dose cytarabine and mitoxantrone in salvage induction, consolidation and maintenance. This is an open-label study, and investigators and subjects are not blinded to the treatment. The reason this is an open-label study is because this is a feasibility trial, and the investigators need to determine whether this regimen is feasible to be tested in larger clinical trials. The assignment of patients will not be randomized, since this is a feasibility trial. The doses of CPI-613 for the induction and consolidation phases of treatment in this study are 500 mg/m^2 or 1,500 mg/m^2 with 20 patients in each cohort for both 500 and 1,500 the study has already accrued 17 patients at 2,000 mg/m^2 cohort; the dose for the maintenance phase of treatment in this study is 2,500 mg/m^2 except for patients who received 500mg/m^2 at induction. Patients receiving 500mg/m^2 at induction will continue with this dose for all phases of therapy including maintenance.

CPI-613 must be diluted from 50 mg/mL to 12.5 mg/mL with D5W (i.e., 1 portion of CPI-613 diluted with 3 portions of D5W) and must be administered IV at a rate of ~0.5 mL/min via a central venous catheter with D5W running at a rate of about 125-150 mL/hr. Please refer to Section 5.4 for methods of administering CPI-613.

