## SCHEMA

This is a Pilot open label trial to establish the feasibility of CPI-613 in combination with high dose cytarabine and mitoxantrone:

*Salvage Induction:* CPI-613 at doses of 1,500 mg/m^2/day will be given over 2 hours on days 1-5. Cytarabine will be given at 3gm/m^2 for age <60 or 1.5 gm/m^2 for age >60 in 500 mL NS over 3 hours every 12 hours for 5 doses starting on day 3. Mitoxantrone will be given at 6mg/m^2 daily for 3 doses given in 50 mL NS over 15 minutes after 1st, 3rd and 5th doses of Cytarabine. A day 14 marrow will be obtained to assess disease response. If there is a response to therapy but residual disease remains patients may receive either a repeated courses identical to the above or a shortened 3 day course with CPI-613 on days 1-3, cytarabine starting on day 2 for 3 total doses and Mitoxantrone after 1st and 3rd doses at the discretion of the treating physician.

There will be 20 patients recruited at a CPI-613 dose of 500mg/m^2/day following the same treatment guidelines outlined above. Individuals recruited to this dose level of CPI-613 will remain on this dose level for consolidation and maintenance therapy.

*Salvage Consolidation:* All responding patients are eligible for consolidation therapy with up to 2 cycles of the shortened 3 course of CPI-613 (same dose as induction cycle), high dose cytarabine and mitoxantrone. Responding patients can be removed from trial at any time to receive a stem cell transplant at the discretion of the treating physician. Patients can move to maintenance following 1, 2 or no cycles of consolidation at the discretion of the treating physician.

*Maintenance Therapy:* Any patient who has completed all planned consolidation therapy (i.e. 0, 1 or 2 cycles) and is not eligible for, faces a significant delay or refuses a stem cell transplant may receive maintenance therapy with CPI-613 at a dose of 2,500 mg/m^2/day over 2 hours on days 1-5 of a 28 day cycle. Patients treated during induction and consolidation at the 500 mg/m^2 dose will receive that dose during maintenance therapy. Patients may continue on maintenance therapy until evidence of disease progression or occurrence of intolerable side effects.

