## 5.0 Treatment Plan

Patients recruited at 500 mg/m^2 will receive this dose for all treatment phases.

Salvage Induction Cycle 1:

The dose of CPI-613 will be 500 mg/m^2/day or 1,500 mg/m^2/day given over 2 hours on days 1-5. Immediately following CPI-613 dosing 50 ml of D5W will be run through the central line. Cytarabine will be given following CPI-613 at 3gm/m^2 for age <60 or 1.5 gm/m^2 for age >60 in 500 mL NS over 3 hours every 12 hours for 5 doses starting on day 3. Mitoxantrone will be given at 6mg/m^2 daily for 3 doses given in 50 mL NS over 15 minutes after 1st, 3rd and 5th doses of cytarabine.

Dose modifications for cytarabine and mitoxantrone are as follows (Please see section 6 for CPI-613 dose modifications):

Hold Cytarabine and notify physician if:

- Bilirubin 1.5-3: Consider Decrease dose by 25%.
- Bilirubin greater than 3: Consider Decrease dose by 50%.
- Cr Cl less than 60 mL/min: Consider dose reduction.
- Hold mitoxantrone and notify physician if:
- Bilirubin greater than 3: Consider Decrease dose by 25%.

All dose modifications are at the discretion of the treating physician.

Salvage Induction Cycle 2 (Optional, at the discretion of the treating physician):

A repeat of the initial cycle as outlined above or at the discretion of the treating physician an abbreviated second cycle can be given. In the abbreviated course CPI-613 is given as above on days 1-3, cytarabine given as above for 3 doses starting on day 2, mitoxantrone given as above after the first and third cytarabine doses.

Salvage Consolidation:

All responding patients are eligible for consolidation therapy with up to 2 cycles of the abbreviated course of CPI-613 at 500 mg/m^2/day or 1,500 mg/m^2/day, high dose cytarabine and mitoxantrone. Responding patients can be removed from trial at any time to receive a stem cell transplant at the discretion of the treating physician. Patients can move to maintenance following 1, 2 or no cycles of consolidation at the discretion of the treating physician.

Maintenance Therapy:

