### **6.0 Dosing Delays/Dose Modifications for CPI-613**

The occurrence of Grade 1 toxicity does not generally require dose modification for subsequent doses for that patient. However, if Grade 2 non-hematologic, non-infectious toxicity develops attributed as at least probably related to CPI-613, treatment can resume only after the Grade 2 toxicity has been reduced to Grade 1 or below, and the dose level for subsequent doses for that patient will be reduced by 25% of the dose at which such Grade 2 toxicity occur. If Grade 3 or 4 non-hematologic, non-infectious toxicity develops, dosing of that patient will be withheld and the patient shall be monitored for recovery from, and reversibility of, such Grade 3 or 4 toxicity. To resume treatment for a patient who has had Grade 3 or 4 toxicity, the Grade 3 or 4 toxicity must be reduced to Grade 1 or below, and the dose level for subsequent doses for that patient will be reduced

to 50% of the dose at which such Grade 3 or 4 toxicity occur. If the reduced dose of CPI-613 results in no toxicity, patients may be dose escalated to the prior dose at the discretion of the treating physician.

Dose adjustments during maintenance therapy will be done as described above with the addition that should patients experience hematologic toxicity  $\geq$  Grade 2 attributed to CPI-613 the next dose of maintenance therapy must be held until the Grade 2 toxicity has been reduced to Grade 1 or below, and the dose level for subsequent doses for that patient will be reduced by 25% of the dose at which such Grade 2 toxicity occurred. If Grade 3 or 4 hematologic toxicity develops, dosing of that patient will be withheld and the patient shall be monitored for recovery from, and reversibility of, such Grade 3 or 4 hematologic toxicity. To resume treatment for a patient who has had Grade 3 or 4 hematologic toxicity, the Grade 3 or 4 hematologic toxicity must be reduced to Grade 1 or below, and the dose level for subsequent doses for that patient will be reduced to 50% of the dose at which such Grade 3 or 4 hematologic toxicity occurred. If the reduced dose of CPI-613 results in no toxicity, patients may be dose escalated to the prior dose at the discretion of the treating physician.

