Terumo syringes  
Monoject syringes  
Glass syringes

Reconstitution and Administration of CPI-613

CPI-613 must be diluted from 50 mg/mL to 12.5 mg/mL with 5% Dextrose Water or D5W (i.e., 1 portion of CPI-613 diluted with 3 portions of D5W) prior to administration. The diluted drug product should be visually inspected for clarity. If haziness or precipitate is observed, do not use the diluted drug product for dosing. After dilution with sterile D5W, the solution is clear and has a pH of 8.4-8.8. The diluted CPI-613 drug product has been found to be stable for 24 hrs at room temperature and refrigeration temperature (Studies STA-010).

CPI-613 must be administered IV, via a central venous catheter that is free flowing, free of air in the dead space, and with D5W running at a rate of about 125-150 mL/hr. This is to minimize vascular irritation, inflammation and acute toxicity of CPI-613 (Study NCL-049). Accidental co-administration of extra air in the dead space of IV catheters during administration of CPI-613 has demonstrated the potential to induce acute toxicity of CPI-613 according to animal studies (Study NCL-049). Also, accidental leakage of CPI-613 into the perivascular space during IV administration, which prolongs exposure of perivascular tissue to CPI-613, can induce significant local inflammation according to animal studies (Studies NCL-027 and NCL-030).

CPI-613 must not be administered as a bolus, but by infusion via a central venous catheter, over a total of 2 hours. All doses of CPI-613 will be administered over 2 hours to simplify PK/PD analysis. The infusion will also minimize potential acute toxicity of CPI-613, according to animal studies (Study NCL-049). The following precautions must be taken when administering CPI-613:

- A. Confirmation of the placement of the IV line to ensure a lack of leakage of CPI-613 into the perivascular space.
- B. Confirmation that the IV line is free flowing, and with D5W running at a rate of about 125-150 mL/hr.
- C. Confirmation that the IV line is free of dead air space.
- D. Rotate the site of administration for different doses of CPI-613.
- E. Dilute CPI-613 drug product with D5W, as instructed in the study protocol.
- F. Administer CPI-613 by infusion, not as a bolus.

G. After administration of CPI-613, “slowly” flush the IV line with ~10 mL of D5W to remove residual CPI-613.

*Request for CPI-613*

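### Above 500 mg/m², the CPI-613 infusion rate in Section 5.3 (about 0.5 mL/min at 12.5 mg/mL) cannot deliver the dose in the required 2 hours

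*Combined protocol and SAP*

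**What the plan says.** Section 5.3 (CPI-613 Dosing) fixes the dilution at 12.5 mg/mL and states that the drug "must be administered IV at a rate of ~0.5 mL/min via a central venous catheter". It names the induction and consolidation doses (500 or 1,500 mg/m²) and the maintenance dose (2,500 mg/m², or 500 mg/m² for the low-dose cohort), and gives one rate for all of them.

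The duration is set elsewhere:

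- Schema, maintenance at 2,500 mg/m²: "over 2 hours on days 1-5 of a 28 day cycle". The Schema also gives 2 hours for induction.
- Section 5.0, induction at 500 or 1,500 mg/m²: "given over 2 hours on days 1-5".
- Section 8.2, Reconstitution and Administration: the drug "must not be administered as a bolus, but by infusion via a central venous catheter, over a total of 2 hours", and "All doses of CPI-613 will be administered over 2 hours to simplify PK/PD analysis".

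Section 8.2 repeats the 12.5 mg/mL dilution but gives no mL/min rate for the drug. Section 5.4, to which Section 5.3 sends the reader for the method of administration, gives neither a drug rate nor a duration.

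**The concern.** Concentration, rate and duration together determine the amount delivered. The plan fixes all three, while the dose varies fivefold between 500 and 2,500 mg/m². At most one dose level can satisfy all three.

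These are operative instructions for an investigational intravenous drug, and both are worded as mandatory. Staff who set the pump from Section 5.3 would run the higher doses for many hours. In induction that would also push back the cytarabine, which follows CPI-613 and is given every 12 hours from day 3. Staff who keep to 2 hours must exceed a mandatory rate several-fold, and nothing in the text says whether that rate was meant as a safety limit. The question is a fair one, because Section 5.4 says that dilution lowers the rate at which drug reaches the body and so limits acute toxicity.

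The mismatch is largest in maintenance. That is also where the Section 5.0 text gives no duration, so a reader of Sections 5.0, 5.3 and 5.4 alone would find a rate for maintenance but no 2-hour rule.

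**Working it through.** **Inputs from the documents**

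- Rate: 0.5 mL/min (Section 5.3).
- Concentration: 12.5 mg/mL (Sections 5.3 and 8.2).
- Duration: 120 min (Schema, Sections 5.0 and 8.2).
- Doses: 500 and 1,500 mg/m² (Sections 5.0 and 5.3) and 2,500 mg/m² in maintenance (Schema, Sections 5.0 and 5.3). Section 10.0 also plans 3 more patients at 2,000 mg/m².

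**Assumption.** BSA of 1.5, 1.8 and 2.2 m². The registration form records BSA, but the documents give no typical value.

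**Step 1: amount delivered in 2 hours.** Volume = 0.5 × 120 = 60 mL. Amount = 60 × 12.5 = 750 mg.

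**Step 2: BSA at which 750 mg is the full dose (no assumption needed).**

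- 500 mg/m²: 750 / 500 = 1.5 m²
- 1,500 mg/m²: 750 / 1,500 = 0.5 m²
- 2,000 mg/m²: 750 / 2,000 = 0.375 m²
- 2,500 mg/m²: 750 / 2,500 = 0.3 m²

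Only the first is an adult value, and Section 3.1 requires age 18 or over.

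**Step 3: size of the mismatch.** Volume = dose × BSA / 12.5. Rate for 2 hours = volume / 120. Time at 0.5 mL/min = volume / 30 hours. Each cell gives BSA 1.5 / 1.8 / 2.2 m².

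| Dose (mg/m²) | Volume (mL) | Rate for 2 h (mL/min) | Multiple of 0.5 mL/min | Time at 0.5 mL/min (h) |
|---|---|---|---|---|
| 500 | 60 / 72 / 88 | 0.50 / 0.60 / 0.73 | 1.0 / 1.2 / 1.5 | 2.0 / 2.4 / 2.9 |
| 1,500 | 180 / 216 / 264 | 1.50 / 1.80 / 2.20 | 3.0 / 3.6 / 4.4 | 6.0 / 7.2 / 8.8 |
| 2,000 | 240 / 288 / 352 | 2.00 / 2.40 / 2.93 | 4.0 / 4.8 / 5.9 | 8.0 / 9.6 / 11.7 |
| 2,500 | 300 / 360 / 440 | 2.50 / 3.00 / 3.67 | 5.0 / 6.0 / 7.3 | 10.0 / 12.0 / 14.7 |

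A wider BSA range of 1.4–2.5 m² gives 5.6–10.0 h at 1,500 mg/m² and 9.3–16.7 h at 2,500 mg/m².

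**Step 4: dose reductions.** Section 6.0 cuts the dose by 25% after Grade 2 toxicity, and "to 50% of the dose at which such Grade 3 or 4 toxicity occur" after Grade 3 or 4. The rates needed for 2 hours after one such reduction (BSA 1.5 / 1.8 / 2.2 m²) are:

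- From 1,500: 1,125 mg/m² needs 1.13 / 1.35 / 1.65 mL/min; 750 mg/m² needs 0.75 / 0.90 / 1.10.
- From 2,500: 1,875 mg/m² needs 1.88 / 2.25 / 2.75 mL/min; 1,250 mg/m² needs 1.25 / 1.50 / 1.83.

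All still exceed 0.5 mL/min.

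**Step 5: other readings.**

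- Loose reading of the approximate sign: 0.75 mL/min delivers 0.75 × 120 × 12.5 = 1,125 mg. At 1,500 mg/m² and BSA 1.5 m² the dose is 2,250 mg.
- Rate applied to undiluted drug at 50 mg/mL: 0.5 × 120 × 50 = 3,000 mg. This breaks the dilution rule, and at BSA 1.8 m² it gives 36, 108 and 180 minutes for 500, 1,500 and 2,500 mg/m², so it does not yield a common 2 hours either.
- The 125–150 mL/hr figure in Sections 5.3, 5.4 and 8.2 is the running D5W line, not the drug.

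None of these reconciles the rate with the duration.

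**The case against.** The arithmetic is not in dispute. The best counter-argument is that the documents show which instruction governs. Two hours appears in the Schema, in Section 5.0 and twice in Section 8.2, where it is said to cover all doses. The 0.5 mL/min figure appears once, is marked approximate and has no stated reason. A pharmacist who noticed the conflict would probably follow the 2-hour rule. No harm is shown: Section 10.0 records 17 patients already accrued at 2,000 mg/m² and 7 at 2,500 mg/m², and the documents report no infusion problem. Even a 14.7-hour infusion is within the 24-hour stability that Section 8.2 gives for diluted drug. No endpoint or sample-size calculation uses the infusion rate.

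Most of this stands. The rate is probably the stray figure, and nothing shows that a patient was under-dosed or that the dose contrast between cohorts was lost. It does not remove the problem, because no text says that 2 hours overrides the rate and the rate is itself worded as mandatory.

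The toxicity argument should be kept modest. Section 8.2 gives PK/PD simplicity as its reason for 2 hours and then adds "The infusion will also minimize potential acute toxicity of CPI-613, according to animal studies". The animal comparison described in Section 1.2 was a 1-hour infusion against a 1-minute bolus in rats. That favours infusion over bolus; it does not favour 2 hours over a slower infusion. The documents therefore cannot rule out that 0.5 mL/min was meant as a cap, and the sponsor has to answer that question.

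**Conclusion.** The concern holds. At 1,500, 2,000 and 2,500 mg/m², the rate in Section 5.3 and the 2-hour duration cannot both be met in any adult, and every infusion at those doses departs from one mandatory instruction. This conclusion needs no BSA assumption.

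The size of the gap does depend on the assumed BSA of 1.5–2.2 m². Keeping to 2 hours means about 3 to 7 times the stated rate, and keeping to the rate means about 6 to 15 hours, across 1,500 to 2,500 mg/m². At 500 mg/m² the two agree at BSA 1.5 m², and the infusion runs to about 2.9 hours at 2.2 m², so that cohort is roughly consistent.

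This is an error in an administration instruction with a bearing on safety, and it should be corrected. No power, sample-size or significance figure is affected.

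**What to change.** First, the sponsor should state whether 0.5 mL/min was intended as a safety cap.

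- If it was not, delete the figure from Section 5.3 and say that the drug is infused at the rate needed to deliver the full calculated dose over 2 hours.
- If it was, keep the rate and amend the 2-hour rule in the Schema, Section 5.0 and Section 8.2. Then check that the longer infusions fit the cytarabine schedule.

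In the first case, a short table of pump rates by dose level and BSA in the pharmacy instructions would help. It should cover 500, 1,500 and 2,500 mg/m², the Section 6.0 reduced doses, and 2,000 mg/m² while Section 10.0 still plans patients there. The table is a convenience, since the rate is simply the volume divided by 120 minutes. Stating the duration in the Section 5.0 maintenance paragraph would close the remaining gap.

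If 2 hours governs, the cost is a wording amendment to one figure and an optional table, with no change to design, sample size or analysis.

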#### **5.4 CPI-613 Administration Guidelines**

Since information on the use of CPI-613 in humans is limited, investigators should be aware of potential AEs and toxicities observed in preclinical studies, as described below.

According to animal toxicology studies, IV administration of CPI-613 can induce reactions at and around the site of administration. These reactions are consistent with local inflammation, which include red/purple/black color, swelling, necrosis, warm to touch, etc. These local reactions occurred more severely when there was accidental leakage of CPI-613 into the perivascular space during IV administration. This is possibly because of low perfusion in the perivascular areas, causing prolonged exposure of local tissues to CPI-613. Therefore, care must be taken to avoid perivascular leakage of CP-613.

CPI-613 must be administered IV by infusion (not bolus), via a central venous catheter that is free flowing, with D5W running at a rate of about 125-150 mL/hr, and free of air in the dead space of the IV catheter. This is to minimize vascular irritation, inflammation and acute toxicity of CPI-613. Accidental co-administration of extra air that is present in the dead space of an IV catheter has been shown to induce excessive acute toxicity of CPI-613 according to animal studies (Study NCL-049).

CPI-613 must be diluted prior to administration, as described in Section 5.3. Dilution of CPI-613 prior to administration reduces the rates of delivery of CPI-613 to the body, thus minimizing the acute toxicity of CPI-613.

Accordingly, the following procedures in administering CPI-613 should be taken to minimize local reactions and acute toxicity of CPI-613:

- A. Confirmation of the placement of the IV line to ensure that there is a lack of leakage of CPI-613 into the perivascular space.
- B. Confirmation that the IV line is free flowing and with D5W running at a rate of about 125-150 mL/hr.
- C. Confirmation that the IV line is free of air in the dead space.
- D. If necessary, rotate the site of administration for different doses of CPI-613.
- E. Dilute CPI-613 drug product with D5W, as instructed in the study protocol.
- F. Administer CPI-613 by infusion, not bolus, as instructed in the study protocol.
- G. Upon completion of administering CPI-613, “slowly” flush the IV line with ~10 mL of D5W to remove residual CPI-613.

Investigators should be aware of the following toxicity observed in animals treated with toxic doses of CPI-613:

1. CPI-613 at the toxicological doses of 30-35 mg/kg (180-210 mg/m^2) induced dose-related incidence of mortality in rats. The cause of death in most rats was due to significant systemic inflammation, and might be related to an over enhancement in the inflammatory responses induced by CPI-613. Deaths due to significant systemic inflammation were also observed in minipigs treated with the minipig toxicological dose of 46.2 mg/kg (i.e., 1617 mg/m^2) of CPI-613. Additionally, CPI-613 at 30 and 35 mg/kg (i.e., 180 and 210 mg/m^2, respectively) in minipigs increased reticulocyte levels, which appeared to be associated with hematopoietic cell proliferation of the spleen, and sternal bone marrow hyperplasia that were secondary to inflammation initiated at the administration site or port. Therefore, investigators should be aware of significant increases in reticulocyte levels, which can be used as an indication of severe inflammation.
2. CPI-613 at 42-55 mg/kg (i.e., 1470-1925 mg/m^2) induced transient vomiting in minipigs.
3. CPI-613 at 42-46.2 mg/kg (1470-1617 mg/m^2, respectively) induced transient and reversible increases in troponin I and creatine kinase (CPK) isoenzyme. The transient and reversible nature of the troponin and CPK isoenzyme results were consistent with necropsy exam and histopathology, which indicated that there was no cardiac damage after the 3-week treatment of different doses of CPI-613.

## **5.5 General Concomitant Medication and Supportive Care Guidelines**

Patients will receive standard prophylactic treatment for drug-related symptoms. Supportive treatments may include anti-emetic, anti-diarrhea, anti-allergic, anti-hypertensive medications, analgesics, antibiotics, allopurinol, and others such as blood products and bone marrow growth factors. The treating physician may utilize marrow growth factors, or blood or platelet transfusions at their discretion. For patients with an ANC  $\geq$  500/mm^3 at the time of CPI-613 administration loperamide can be administered as a premedication at a dose of 2 to 4 mg PO 30 minutes prior to CPI-613.

